Study Title: A safety study of intravitreal PP-001 in patients with chronic, non-infectious uveitis having chronic inflammation

Study Objectives:

Primary Objective

- To assess the safety and tolerability of ascending doses of PP-001 in patients with chronic, non-infectious uveitis when administered as a single intravitreal injection of 0.3 µg, 0.6 µg and 1.2 µg with the option of an addition cohort with a dose of 2.1 µg PP-001

Secondary Objectives

- To assess the improvement of inflammation in patients with chronic, non-infectious uveitis after ascending doses of PP-001 when administered as a single intravitreal injection of 0.3 µg, 0.6 µg and 1.2 µg with the option of an addition cohort with a dose of 2.1 µg PP-001
- To evaluate the pharmacokinetics of PP-001 in patients with chronic, non-infectious uveitis when administered as a single intravitreal injection of 0.3 µg, 0.6 µg and 1.2 µg with the option of an addition cohort with a dose of 2.1 µg PP-001

Study Population:

Inclusion Criteria

1. Male or female patients without childbearing potential older than 18 years of age who have diagnosis of chronic posterior uveitis, intermediate uveitis or panuveitis.
2. Good general state of health (mentally and physically). Laboratory parameters and vital signs of patients must be within the normal ranges and patients must not have a diagnosis of any acute or chronic illness except uveitis.
3. A signed and dated written informed consent form.
4. A signed and dated written data protection consent form.
5. Male patients must ensure that one highly effective method combined with an acceptable method of contraception is used for the entire duration of the study, from first dose up to the study follow-up visit, and refrain from fathering a child in the 3 months following the last study drug administration. Male patients must agree with their female partners prior to screening to use the above specified methods of contraception while receiving protocol-specified medication, and for 3 months after stopping the medication. Female patients must be of non-childbearing potential. The definition of non-childbearing potential includes the following:
 - Surgically sterile (e.g., hysterectomy with or without oophorectomy; fallopian tube ligation; endometrial ablation), at least 30 days prior to signature of the Informed Consent form
 - At least 3 years post-menopause (i.e., 4 years post last menstrual period), or menopause confirmed by follicle-stimulating hormone (FSH) testing.

6. Have diagnosis of chronic posterior uveitis, intermediate uveitis or panuveitis (as defined by the Standardization of Uveitis Nomenclature Working Group [Jabs et al., 2005]) in at least one eye. For patients with panuveitis, the anterior component of inflammation must be less than the posterior component. The investigator to his best knowledge must rule out any suspected masquerade syndrome or infection prior to study entry.
7. Have chronic, posterior uveitis, intermediate uveitis or panuveitis requiring treatment
8. Have media clarity, pupillary dilation and patient cooperation sufficient for adequate visualization of the optic nerve in the study eye.
9. Have been receiving an adequate therapy of e.g. systemic corticosteroid treatment or immunosuppressive therapy (e.g. azathioprine, methotrexate, cyclosporine, mycophenolate, tacrolimus) or any combination thereof. Any systemic therapy at study start should *be continued throughout the study*.
10. Best-corrected Early Treatment Diabetic Retinopathy Study (ETDRS) visual acuity of 10 letters or better (approximately 1/35 or 0.032) but equal or less than 50 letters (approximately 20/100 or 0.2) in the study eye.
11. Best-corrected ETDRS visual acuity of 50 letters or better in the fellow eye (approximately 20/100 or 0.2)

Exclusion Criteria

1. Patients in whom media opacities (cornea, anterior or posterior synechia, cataract, vitreous haze and others) of either eye preclude investigation and documentation of the posterior pole and intravenous fluorescein angiography, or optical coherence tomography evaluation in the study eye.
2. Patients receiving any local biologicals.
3. Treatment with cyclophosphamide or chlorambucil.
4. Intravitreal injections (including but not limited to anti-vascular endothelial growth factors) 60 days prior to the baseline.
5. Posterior subtenon's injection or orbital floor injection of steroids 90 days prior to Baseline.
6. Any implantable corticosteroid-eluting device (Ozurdex, Iluvien, Retisert, triamcinolone intravitreal implant, fluocinolone intravitreal implant) in the study eye, with the following exceptions:
 - If the device had been removed more than 90 days prior to Day 0 of this study, the eye will be eligible for PP-001-1001.
 - If Ozurdex had been implanted 6 months before Day 0 of this study, the eye will be eligible for PP-001-1001.
 - If Iluvien or Retisert had been implanted 3 years before Day 0 of this study, the eye will be eligible for PP-001-1001.
7. Intraocular surgery within 90 days prior to Day 0 in the study eye.
8. Capsulotomy within 30 days prior to Day 0 in the study eye.
9. History of vitreoretinal surgery or scleral buckling within 90 days prior to Day 0 in the study eye.
10. Any ocular surgery (including cataract extraction or capsulotomy) of the study eye anticipated within the first 60 days following Day 0.
11. Intraocular pressure (IOP) ≥ 25 mmHg in the study eye (glaucoma patients maintained on no more than one topical medication with IOP < 25 mmHg are allowed to participate).
12. Ocular hypotonia (IOP less than 6 mmHg).

13. Pupillary dilation inadequate for quality fundus photography in the study eye.
14. Aphakia or anterior chamber lens in the study eye.
15. Visible scleral thinning, scleral ectasia or keratoconus in the study eye.
16. Presence of any ocular malignancy.
17. Ocular or periocular infection in either eye or the use of systemic antibiotics.
18. Participation in other investigational drug or device clinical trials within 90 days prior to Day 0, or planning to participate in other investigational drug or device clinical trials within 180 days following Day 0. This includes both ocular and non-ocular clinical trials.
19. Female patients who are of childbearing potential or who are pregnant.
20. Use of any anticoagulant or thrombocyte aggregation inhibiting agent (marcumar, warfarin, heparin, enoxaparin, apixaban, rivaroxaban, pentosanpolysulfate, dabigatran, aspirin, and others) less than 14 days prior to injection visit (Day 0).
21. Known allergy or hypersensitivity to the study medication, any component of the delivery vehicle, any corticosteroids or any diagnostic agents used during the study (e.g., fluorescein, dilation drops, antibiotic drops, povidone).
22. Patients with diagnosis of any acute or chronic systemic illness other than uveitis

Duration of Study: Total duration of study for each patient will be 8 weeks or less (from screening to last follow-up).

Drug Products: PP-001 will be supplied as a sterile concentrate solution in a 2 ml vial and will be diluted according to dose as specified in the pharmacy manual.

Study Drug Assignment: Patients will be dosed in ascending order with 0.3, 0.6, 1.2 or 2.1 µg PP-001 depending on the cohort to which they are assigned.

Duration of Treatment: Patients will receive a single dose of PP-001.

Study Drug Administration: PP-001 will be administered as a single intravitreal injection, which will be performed under sterile conditions in an operating room setting. For safety reasons an emergency pars plana vitrectomy aiming at removal of injected drug will be available in case of a severe adverse event including, but not limited to, acute loss of visual acuity or acute inflammatory or toxic response to injection. It is therefore mandatory for patients to remain in the hospital for at least 4 hours after the injection procedure.

Blinding: This is an open-label study.

Study Design: This prospective, multi-centre, open-label, non-randomized, consecutive study will be conducted in accordance with the European Union (EU) Clinical Trial Directive 2001/20/EC and 2005/28/EC, The Medicines for Human Use (Clinical Trials) Regulations 2004 and current amendments, the Declaration of Helsinki (revised version of Edinburgh, Scotland 2000), Good Manufacturing Practice (GMP), Good Clinical Practice (GCP) and the current national regulations and guidelines, approved by both the local ethics committee and regulatory authority. Eighteen patients older than 18 years of age will be enrolled and receive a single intravitreal injection of PP-001. Patients must have chronic, posterior uveitis, intermediate uveitis or panuveitis requiring treatment and have been receiving an adequate therapy of e.g. systemic corticosteroid treatment or immunosuppressive therapy (e.g. azathioprine, methotrexate, cyclosporine, mycophenolate, tacrolimus) or any combination thereof. Any systemic therapy at study start should be continued throughout the study. Patients must have best-corrected Early Treatment Diabetic Retinopathy Study (ETDRS) visual acuity of 10 letters

or better (approximately 1/35 or 0.032) but equal or less than 50 letters (approximately 20/100 or 0.2) in the study eye.

The study will involve eight inpatient visits (Screening, Baseline, the day of injection [Day 0] and Days 2, 7, 14, 21 and 28) and telephone calls on Day 1 and on Day 40.

Patients will be divided into three cohorts of four patients. Patients will receive the following treatments administered as a single intravitreal injection:

- Cohort 1 will receive 0.3 µg of PP-001
- Cohort 2 will receive 0.6 µg of PP-001
- Cohort 3 will receive 1.2 µg of PP-001

The patients within a cohort will be dosed consecutively with a minimum time interval of 7 days between the start of injection of the previous patient and start of injection of the next patient. The results from each dosing day will be reviewed before progressing with the subsequent dosing day. The next cohort will only commence with dosing after the previous cohort has completed all study sessions up to Day 28 and no safety issues have been identified after being reviewed by the safety data management board (SDMB).

After 12 patients have been treated in the three cohorts and after all patients have finished the last follow up an interim analysis by the SDMB will be conducted to identify potential safety issues and to determine the highest tolerable dose. If no safety issue can be identified, then a fourth, higher dose will be given to a cohort of four patients (Cohort 4). The dose for a potential Cohort 4 will be 2.1 µg of PP-001.

If safety issues are identified in any of Cohorts 2, 3 or 4, two additional patients will receive the next lower dose.

Statistical Considerations:

- Sample Size: Eighteen patients will be enrolled in the study. No power calculations will be performed and the sample size is based on the requirements of the study design.
- Treatment Comparison of Interest: a comparison will be made between the cohorts with regard to safety tolerability and efficacy.

Interim Analysis: the results from each dosing day of the first cohort will be reviewed before progressing with the subsequent dosing day. Dosing of the next cohort will only commence after the previous cohort has completed all study sessions up to Day 28 and no safety issues have been identified after being reviewed by the SDMB.

Analysis Populations

- *Intent-to-treat (ITT) Analysis Set*: all patients regardless of whether or not the patient received study drug
- *Per-protocol Analysis Set*: all ITT Analysis Set patients who have no major protocol deviations, and who complete the study up to the end of the post-study assessments
- *Safety Analysis Set*: all patients who receive any amount of study drug. All safety analyses will be conducted in this population

- *Pharmacokinetic Analysis Set:* all patients who receive any amount of study drug will be included in the formal analysis of pharmacokinetic parameters providing they have at least one evaluable pharmacokinetic sample

Variables for Analysis:**Primary**

- Safety parameters (i.e., changes in clinical signs and symptoms from ophthalmic exam, and AEs)

Secondary

- Improvement of inflammation or of any other parameter determined at the ophthalmic examination following the injection of PP-001
- The concentration of PP-001 in plasma at Screening, 4 h ± 1 h after dosing and on Day 2

Safety analysis

The incidence of treatment-emergent adverse events (TEAEs), SAEs, deaths and discontinuations of study drug due to an AE or SAE will be summarized by System Organ Class and Preferred Term according to the Medical Dictionary for Regulatory Activities, by relationship to study drug, and by severity. The incidence of potentially clinically significant vital signs will be summarized.

Pharmacokinetic analysis

The concentration of PP-001 in plasma will be measured in blood samples taken at Screening, 4 h ± 1 h after dosing and on Day 2.

Table 1. Schedule of Assessments and Procedures

| Phase | Screening | Baseline ⁱ | Pre injection | Post injection | Telephone call ^a | Safety visits | | | | | Telephone call ^a |
|--|------------------|-----------------------|---------------|------------------|-----------------------------|---------------|-----------|------------|------------|-------------------------|-----------------------------|
| Day | -14 up to dosing | -7 up to dosing | 0 | 0 | 1 | 2 | 7 +/-1 | 14 +/-1 | 21 +/-1 | 28 ^h +/-1 | 40 |
| Electroretinography | | X | | | | | | X | | X | |
| Fluorescein angiogram | X | | | | | | | | | X | |
| Optical coherence tomography | | X | | | | X | X | X | X | X | |
| Best corrected visual acuity (ETDRS) | X | X | | | | X | X | X | X | X | |
| Visual field (computerized, 30°) | | X | | | | | X | | | X | |
| Visually evoked cortical potential | X | | | | | | | | | X | |
| Intraocular pressure | X | X | | X ^b | | X | X | X | X | X | |
| Slit lamp examination ^c | X | X | X | X ^b | | X | X | X | X | X | |
| Dilated fundoscopy ^d | X | X | | X ^b | | X | X | X | X | X | |
| Study drug injection | | | | X | | | | | | | |
| Blood sampling for PK analysis | X | | | X ^{b,e} | | X | | | | | |
| Corneal endothelial microscopy | | X | | | | | X | | | X | |
| Fundus photography | | X | | | | | | | | X | |
| Amsler grid | | X | | | | X | X | X | X | X | |
| Medical and ophthalmic histories | X | X | | | | | | | | | |
| Vital signs ^f | X | X | X | | | X | X | X | X | X | |
| Twelve-lead electrocardiogram | X | | | | | | | | | X | |
| Laboratory assessments | X | | | | | | | | | X | |
| Patient-reported outcomes ^g | | X | | | | | | | | X | |
| Concomitant medication | X | X | X | | X | X | X | X | X | X | |
| Serious medical events | X | X | X | X | X | X | X | X | X | X | X |
| Adverse events | X | X | X | X | X | X | X | X | X | X | X |

ETDRS: Early Treatment of Diabetic Retinopathy Study; PK: Pharmacokinetic

a. Standardized questions including (but not limited to): pain, blurred vision, change in visual acuity, redness of the eye

b. Examination will be performed after administration of study drug

c. Conjunctiva, cornea, anterior chamber including grading of cells and haze (Standardization of Uveitis Nomenclature Working Group), lens (Lens opacities classification system II) and vitreal haze (Standardization of Uveitis Nomenclature Working Group)

d. Including slit lamp biomicroscopy of the fundus

e. Day 0 blood sample will be taken 4 h ± 1 h after injection

f. Blood pressure and heart rate

g. National Eye Institute Visual Functioning Questionnaire 25 (VFQ-25), SF36™ Health Survey Version 2 (SF-36v2) and EuroQol-5 Dimensions Health Questionnaire (EQ-5D)

h: for visit 28 option to perform examinations to 2 consecutive days;

i: in case screening visit and baseline visit are on the same day (-7 up to dosing), examinations scheduled for both visits need only to be performed once and may be used for both study visits

LIST OF ABBREVIATIONS AND DEFINITIONS OF TERMS

| Abbreviation | Definition |
|---------------------|--|
| AE | Adverse event |
| AUC | Area under the plasma concentration time curve |
| BP | Blood pressure |
| CS | Clinically significant |
| C _{max} | Maximum plasma concentration |
| DHODH | Dihydroorotate dehydrogenase |
| EAU | Experimental autoimmune uveitis |
| ECG | Electrocardiogram |
| eCRF | Electronic case report form |
| ETDRS | Early Treatment of Diabetic Retinopathy Study |
| EU | European Union |
| GCP | Good clinical practice |
| GLP | Good laboratory practice |
| h | Hours |
| hERG | Human ether-à-go-go-related gene |
| HR | Heart rate |
| IC ₅₀ | Half-maximal inhibitory concentration |
| ICH | International Conference on Harmonization |
| IEC | Independent ethics committee |
| ITT | Intent-to-treat |
| IFN- γ | Interferon gamma |
| IL-17 | Interleukin 17 |
| IOP | Intraocular pressure |
| K ₃ EDTA | Tri-potassium ethylenediaminetetraacetic acid |
| MedDRA | Medical Dictionary for Regulatory Activities |
| NCS | Not clinically significant |

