1.3.3 Non-Clinical Safety and Toxicology

Non-clinical safety and toxicology studies included acute (intravitreal) and repeated dose (intravenous) toxicity testing in rabbits and rats, and *in vitro* genotoxicity testing in bacterial and mammalian cells. All pivotal non-clinical studies were conducted in a country that is a member of the Organisation for Economic Co-operation and Development (OECD) Mutual Acceptance of Data program in accordance with the OECD Test Guidelines and Principles of Good Laboratory Practice (GLP) and respective ICH and Committee for Medicinal Products for Human Use guidance.

When PP-001 was given via the systemic route the no-observed-effect level (NOEL) in a 14-day repeated dose toxicity study in rats was 1 mg/kg body weight, which was the highest dose tested. In this study, the detected systemic exposure was several hundred fold higher than the expected exposures after intravitreal therapeutic doses in humans and thus provides an adequate safety margin with respect to systemic toxicity.

In an ocular extended single dose toxicity study conducted in rabbits (12 eyes dosed in 6 animals), intravitreal injection of PP-001 was shown to be safe with a no-observed-adverse-effect-level (NOAEL) of 10 µg/eye over an observation period of 15 days. Higher doses (20 and 30 µg/eye) resulted in adverse changes in retina (retina detachment and retinal tear, focal exudation etc.), choroid (vessel enlargement, choroidal exudates) and vitreous (floaters). There was no test item related intraocular pressure (IOP) abnormality or any other finding in body weight change, food and water consumption and clinical pathology in any dose group observed during the course of the study. Toxicokinetic analysis of blood plasma after dosing with 30 µg in each eye established that maximum plasma concentration (43.5 ng/ml) was reached at 4 h post dosing and PP-001 was not detectable after 8 h post dosing. There was no test item related intraocular pressure (IOP) abnormality or any other finding in body weight change, food and water consumption and clinical pathology in any dose group observed during the course of the study.

PP-001 did not show genotoxic potential in *S. typhimurium* tester strains and a mouse lymphoma assay. No phototoxic risk is indicated since PP-001 does not absorb light at relevant wavelengths.

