6.3 Physical Examination

A complete physical examination will be performed by the Investigator at Screening. At the time points specified in Table 1, subsequent directed physical examinations will be performed according to standard institutional practices and must be documented in source documents.

Body weight and height will be measured at Screening only.

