9.4 Criteria for Evaluation

9.4.1 Safety Analysis Variables

Safety and tolerability of PP-001 as measured by treatment-emergent AEs (TEAEs) and vital signs.

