3.6 Safety endpoints

The safety endpoints are the following:

- Adverse Events (AEs);
- Vital Signs (blood pressure, heart rate);
- Electrocardiogram (ECG);
- Laboratory parameters (hematology, biochemistry and urinalysis).

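### Vital signs are a named safety variable, but none is scheduled between the pre-injection reading and Day 2, so an asymptomatic, transient acute change would not appear in the scheduled data

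*Protocol*

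**What the plan says.** Protocol Section 3 names vital signs and adverse events (AEs) as the means of assessing safety. Section 9.4.1 defines the safety variables as "Safety and tolerability of PP-001 as measured by treatment-emergent AEs (TEAEs) and vital signs". Section 9.6 plans vital-sign summaries by visit and a worst post-baseline value. SAP 3.6 lists vital signs, ECG and laboratory parameters as safety endpoints, and SAP 8.3 with Table 14.3.3.1 summarises vital signs and their change from baseline.

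The columns of Protocol Table 1 are, in order: Screening, Baseline, Pre injection, Post injection, Day 1 call, Days 2, 7, 14, 21 and 28, and Day 40 call. The relevant rows are:

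- "Vital signs ^f | X | X | X | | | X | X | X | X | X"
- "Twelve-lead electrocardiogram | X | | | | | | | | | X"
- "Laboratory assessments | X | | | | | | | | | X"

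The SAP 3.2 schedule has the same entries for these three rows. The Post-injection column does contain intraocular pressure, slit lamp, fundoscopy, a PK sample at 4 h ± 1 h, and AE collection. Patients must stay in hospital at least 4 hours (synopsis; Section 6.1). Sections 3 and 5.2.2 require the results of each dosing day to be reviewed before the next dosing day.

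In the rabbit study of Section 1.3.3 (30 µg in each eye), the plasma maximum of 43.5 ng/ml "was reached at 4 h post dosing and PP-001 was not detectable after 8 h post dosing". Section 1.3.2 gives rabbit half-lives of 5 to 6 h in blood and 12 to 21 h in ocular tissue.

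On physical examination, Section 6.3 says: "At the time points specified in Table 1, subsequent directed physical examinations will be performed". Table 1 has no such row.

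**The concern.** This is the first human exposure to the drug, and vital signs are one of only two safety variables named in Section 9.4.1. The protocol's animal data place any plasma exposure in the first hours after injection. The schedule draws blood for PK at that time, with the patient already in hospital, but takes no blood pressure or heart rate beside it.

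Two things follow. First, Table 14.3.3.1 and the worst post-baseline value will contain no scheduled reading from the period when an acute effect is most plausible, so normal values there say little about that period. Second, the dosing-day review that is meant to protect the next patient has no post-dose vital sign among its dosing-day results.

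**Working it through.** The plan states no figure for this point, so the check sets the schedule against the protocol's own kinetics.

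**1. First scheduled post-dose measurement (Table 1; SAP 3.2)**

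| Measurement | Last before dosing | First after dosing |
|---|---|---|
| Blood pressure, heart rate | Day 0, pre-injection | Day 2 (48 h) |
| ECG | Screening | Day 28 (672 h) |
| Laboratory panel | Screening | Day 28 (672 h) |
| PK sample | Screening | 4 h ± 1 h |

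**2. Half-lives elapsed.** Fraction remaining = 2^(−t / half-life), using the rabbit blood half-life of 5 to 6 h.

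- 48 h: 48/6 = 8.0 and 48/5 = 9.6 half-lives; 2^−8 = 0.39% and 2^−9.6 = 0.13%.
- Counted from the 4 h peak (44 h elapsed): 44/6 = 7.3 and 44/5 = 8.8 half-lives, or about 0.6% and 0.2% of the peak.
- 672 h: 672/6 = 112 and 672/5 = 134 blood half-lives. Even on the ocular half-life, 672/21 = 32 and 672/12 = 56. Effectively nothing remains.

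**3. Sensitivity of the Day 2 figure**

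- If plasma decline followed the ocular half-life: 48/12 = 4.0 half-lives (6.25%) and 48/21 = 2.3 half-lives (20.5%).
- The SAP 3.2 schedule prints a one-day window for Day 2; Protocol Table 1 prints none. A visit at 24 h gives 24/5 = 4.8 half-lives (3.6%) and 24/6 = 4.0 half-lives (6.25%).
- Rabbit peak of 43.5 ng/ml falling to 10 ng/ml: 4 + 5 × log2(4.35) = 14.6 h and 4 + 6 × log2(4.35) = 16.7 h. Section 1.3.3 itself reports no detectable drug after 8 h. Either way the rabbit window closes well before 48 h.

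**4. Expected size of human exposure.** Scaling the rabbit peak linearly by dose (43.5 ng/ml per 60 µg per animal; assumed, no body-size correction), peak = 43.5 × dose / 60.

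| Dose | Peak | 10 ng/ml ÷ peak | 58 ng/ml ÷ peak |
|---|---|---|---|
| 0.3 µg | 0.22 ng/ml | 46 | 267 |
| 0.6 µg | 0.44 ng/ml | 23 | 133 |
| 1.2 µg | 0.87 ng/ml | 11.5 | 67 |
| 2.1 µg | 1.52 ng/ml | 6.6 | 38 |

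The 10 ng/ml is the assay detection limit in Section 3.2. The 58 ng/ml is the lowest active concentration in Section 1.3.1.

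**5. What the reviews can see.** The results of a dosing day include the post-injection eye examination and AEs, but no post-dose blood pressure or heart rate. With the 7-day minimum gap, the Day 2 reading should exist before the next patient is dosed. At that minimum gap the four patients of a cohort are dosed on days 0, 7, 14 and 21, so all four can be dosed before the first patient's Day 28 ECG and laboratory panel. The next cohort does wait for Day 28.

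**The case against.** The light systemic schedule has a stated basis. Section 3.2 expects plasma levels near or below 10 ng/ml and no systemic effects, and Section 3.1.1 expects negligible exposure at the starting dose. Section 1.3.1 reports no hERG signal well above intended exposure and no adverse safety-pharmacology findings in rats at 1 mg/kg intravenously. The scaling above agrees. The primary endpoint is ophthalmic findings and AEs, and both are assessed after injection. This stands, and it limits the weight of the point. It remains an expectation from animals, and a first-in-human study exists to check such expectations.

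Several stronger readings are tempting, but the documents do not support them:

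- *That an acute systemic effect could not be detected at all.* AEs are collected post-injection and at the Day 1 call. Section 6.4 allows more frequent blood pressure and heart rate if clinically warranted, and Section 6.6 allows extra laboratory tests. What is missed is an asymptomatic, transient change.
- *That the measurements miss a known period of drug in human plasma.* That window is extrapolated from rabbits given 60 µg per animal; in patients there may be no measurable exposure.
- *That the trial plans to conclude there is no systemic effect.* Section 3.2 states this as an expectation; neither document plans it as a conclusion.
- *That physical examination is a safety endpoint lost by the same timing.* SAP 3.6 does not list it, and SAP 8.5 only lists the data. The missing Table 1 row is a cross-reference fault.
- *That the ECG should move to 4 h and a laboratory panel be added on Day 2.* Section 6.5 specifies a set of three recordings, and moving it gives up the only end-of-study ECG. A Day 2 panel would come after the same 8 to 9.6 half-lives, so the timing argument does not support it.

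**Conclusion.** The point holds in a limited form. For every patient in every cohort, the scheduled vital signs skip the interval from injection to Day 2, and the scheduled ECG and laboratory panel skip the interval to Day 28. The scheduled data therefore cannot show an asymptomatic, transient acute change.

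The schedule facts are certain. The figure of 8 to 9.6 half-lives assumes that human plasma kinetics resemble the rabbit's and that Day 2 falls at 48 h. Under the less favourable assumptions in the working, between 3.6% and 20.5% could remain at the first reading. Given the expected exposure, the practical weight is moderate. The case for acting is that the omission concerns a named safety variable and costs very little to close.

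**What to change.** - Add blood pressure and heart rate to the Post-injection column of Protocol Table 1 and of the SAP 3.2 schedule, at the existing 4 h ± 1 h blood draw. The same-day pre-injection reading is already collected for comparison.
- Include that time point in SAP 8.3 and Table 14.3.3.1.
- Keep the Day 28 ECG and laboratory panel, and state in the SAP that, as scheduled, these two endpoints address only delayed or persistent effects.
- Reconcile Section 6.3 with Table 1, which has no physical examination row.

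SAP 4.8 says the study closes at cohort 3. If dosing is already finished and collection cannot change, the SAP and the report should say that vital signs also have no scheduled reading between injection and Day 2.

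The cost is a few minutes per patient during a stay that is already mandatory, one added eCRF field, and a matching amendment in each country protocol (the SAP revision history names Austria, Germany, Belgium, the Netherlands and the United Kingdom). No extra blood is needed.
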